**Total number of T1 Gd-enhanced lesions detected by brain MRI at Weeks 24, 48, and 96**

The analyses will include patients who have an interpretable MRI at the time point of interest. The following analyses will be presented:

- Number and percentage of patients having 0, 1, 2, 3, and greater than 3 lesions at weeks 24, 48, and 96.
- The unadjusted and adjusted rates of lesion occurrence at weeks 24, 48, and 96 combined will be calculated:
  - The unadjusted rate will be the ratio of the total number of T1 Gd-enhanced lesions to the total number of interpretable MRI scans.
  - The adjusted rate will be derived using a negative binomial model. The dependent variable in the model will be the total number of T1-Gd-enhanced lesions. The model will be adjusted for the following baseline covariates: Gd lesion (present or not), EDSS score ( $< 2.5$  vs.  $\geq 2.5$ ), and number of previous DMTs (1 vs.  $>1$ ). In order to account for patients potentially receiving varying numbers of brain MRI scans during the study, the log-transformed number of brain MRI scans received will be included in the model as an “offset”.

- Histogram of the count (0, 1, 2, 3, >3) of T1 Gd-enhanced lesions at Weeks 24, 48, and 96, and during all visits combined will be produced.

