6.5.4 Analysis Methods

The proportion of patients who are free from a protocol-defined event during Week 96 (the primary efficacy endpoint) will be calculated, and the two-sided 95% CI will be presented. Data from any unscheduled visit within each respective 24-week interval will be included for this endpoint. Similar analyses will be applied to the proportions of patients who are free from a protocol-defined event during Weeks 24 and 48.

The annualized relapse rates by Week 96 will be analyzed using negative binomial model, adjusting for the number of previous DMTs used and including the log-transformed year of drug exposure time as an “offset” variable. The adjusted annualized relapse rate and the two-sided 95% CI for the relapse rate will be presented.

The Kaplan-Meier estimator (i.e., the product limit estimator) will be used to estimate the survival function for time-to-event data (e.g., time to protocol-defined event; time to onset

of first relapse; time to onset of CDP for at least 24 weeks). The proportion of patients with an event and of those censored will be reported; the median survival time and its 95% CI will be presented.

The total number of T1 Gd-enhanced lesions will be calculated as the sum of the individual number of T1 Gd-enhanced lesions at Weeks 24, 48, and 96. Data from other unscheduled assessments will not be included in this summary or analysis. A negative binomial model will be used to estimate the rate of lesion occurrence. In order to account for patients receiving varying numbers of brain MRI scans during the study, the log-transformed number of brain MRI scans received will be included in the model as an “offset” variable for appropriate computation.

The change from baseline in total T2 lesion volume as detected by brain MRI to Weeks 24, 48, and 96 will be analyzed through a mixed model with repeated measure (MMRM), adjusting the following covariates: baseline score and the number of previous DMT use.

The total number of new and/or enlarging T2 lesions will be calculated as the sum of the individual number of new and/or enlarging T2 lesions at Weeks 24, 48, and 96. Data from unscheduled assessments will not be included in this summary or analysis. The analysis model will be similar to that used for the total number of T1 Gd-enhanced lesions.

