Appendix 1 Schedule of Activities (cont.)

Visit Number	Screening	Treatment Period						Safety Follow-up Visit ^b	Early Withdrawal Visit ^c	Unscheduled Visit (due to relapse) ^d
	1	2	3	4	5	6	7			
Week	-4 ^a	-	2	24	48	72	96			
Study Day (window in days)	-28	1 Baseline	15 (\pm 2)	169 (\pm 14)	337 (\pm 14)	505 (\pm 14)	673 (\pm 14)			
Brain MRI ^r		x ^s		x ^o	x ^o		x	x ^c		
Recording of potential relapses		x	x	x	x	x	x	x	x	x
Adverse event assessment ^t		x	x	x	x	x	x	x	x	x
Concomitant treatment review		x	x	x	x	x	x ^u	x	x	x
Methylprednisolone and antihistamine premedication ^v		x	x	x	x	x				
Ocrelizumab administration ^w		x	x	x	x	x				

β -hCG = beta human chorionic gonadotropin; eCRF = electronic Case Report Form; EDSS = Expanded Disability Status Scale; HBcAb = hepatitis B core antibody; HBsAg = hepatitis B surface antigen; HBV = hepatitis B virus; HepCAb = hepatitis C antibody; IRR = infusion-related reaction; IV = intravenous; MRI = magnetic resonance imaging; MS = multiple sclerosis; PCR = polymerase chain reaction; PML = progressive multifocal leukoencephalopathy; PRO = patient-reported outcome; QC = quality control.

^a The screening period will last up to 4 weeks, but it may be prolonged for up to 8 weeks for relevant clinical, administrative, or operational reasons.

^b The Safety Follow-up Period will begin when the patient *completes their infusion at Week 72 or discontinues from treatment early*. Patients will be assessed *at 24 weeks (at Week 96)*. If the peripheral blood B-cell count remains depleted *after 6 months from the date of the last infusion, the investigator may want to continue monitoring the B-cell count until it has returned to the baseline value or to the lower limit of the normal range, whichever is lower*. During the Safety Follow-up Period, patients who receive other B-cell targeted therapies will only be followed for an additional period of approximately 24 weeks from the start of the alternative MS treatment.

^c When a patient discontinues treatment, all assessments must be completed/obtained, except for MRI if done within the past 8 weeks unless clinically indicated.

Ocrelizumab—Genentech, Inc.

76/ Protocol MN30035, Version 5

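### The offset for the adjusted T1 Gd lesion rate counts scans received, not interpretable scans, so applied as written it lowers the rate by about the share of unreadable scans

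*SAP*

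**What the plan says.** The subsection on T1 Gd-enhanced lesions in SAP 4.4.2 sets out one quantity in two forms: "The unadjusted and adjusted rates of lesion occurrence at weeks 24, 48, and 96 combined will be calculated".

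- **Unadjusted rate.** "The unadjusted rate will be the ratio of the total number of T1 Gd-enhanced lesions to the total number of interpretable MRI scans".
- **Adjusted rate.** A negative binomial model. "The dependent variable in the model will be the total number of T1-Gd-enhanced lesions". Covariates are baseline Gd status, EDSS group and number of previous DMTs. For the offset, "the log-transformed number of brain MRI scans received will be included in the model".
- **Who is analysed.** "The analyses will include patients who have an interpretable MRI at the time point of interest".

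Protocol 6.5.4 uses the same offset, based on scans received, and defines the count as the "sum of the individual number of T1 Gd-enhanced lesions at Weeks 24, 48, and 96". It does not mention interpretability. The SAP adds that condition to the unadjusted denominator and to the selection of patients, but not to the offset. The next SAP subsection applies a similar analysis to new or enlarging T2 lesions.

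**The concern.** The offset in a count model is the denominator of the rate, so it should count the scans on which a lesion could have been counted. Here the two forms of the same rate rest on different scan counts.

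The sentence on interpretable MRI does not close the gap, because it selects patients and not scans. A patient with one readable and two unreadable scans stays in the analysis, with lesions from one scan and an offset of log 3.

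Any error from this source runs one way. An unreadable scan can enlarge the offset but cannot enlarge the count, so the adjusted rate is either right or too low, and too low is the favourable direction.

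**Working it through.** **Plan's own figure.** The documents state no lesion rate, scan count or share of unreadable scans, so there is nothing to reproduce. What follows is the size of the effect under stated assumptions.

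**Algebra.** Let *L* be the lesion total, *R* the scans received at Weeks 24, 48 and 96, and *u* the share of *R* that is unreadable. Interpretable scans are *I* = (1 − *u*)*R*. For an intercept-only rate,

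rate on received ÷ rate on interpretable = (*L*/*R*) ÷ (*L*/*I*) = *I*/*R* = 1 − *u*.

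Example, assuming 600 patients with three scans each: *R* = 600 × 3 = 1800. At *u* = 5%, *I* = 1710. At a true rate of 0.05 per scan, *L* = 0.05 × 1710 = 85.5, and 85.5/1800 = 0.0475, which is 0.95 of the true rate.

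**Direction in the negative binomial model.** With dispersion *k* held fixed, each term of the intercept score is (*y* − μ)/(1 + *k*μ), where μ is the rate times the scans counted. Each term falls as μ rises. A larger offset must therefore lower the fitted rate.

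**Simulation with *k* estimated.** 200 data sets per setting; none of these settings comes from the documents:
- 600 patients, of whom 15% have only one or two scans received
- gamma heterogeneity with shape 0.3
- unreadability unrelated to lesions
- no covariates

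Median ratio of the rate with the received offset to the rate with the interpretable offset:

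| Assumed share unreadable | 1 − *u* | True rate 0.02 | True rate 0.05 | True rate 0.2 |
|---|---|---|---|---|
| 1% | 0.99 | 0.9903 | 0.9908 | 0.9916 |
| 2% | 0.98 | 0.9813 | 0.9807 | 0.9821 |
| 5% | 0.95 | 0.9521 | 0.9526 | 0.9538 |
| 10% | 0.90 | 0.9051 | 0.9046 | 0.9059 |

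The received offset gave the lower rate in 99.5–100% of data sets. The ratios sit slightly above 1 − *u*, partly because a patient with no readable scan leaves the analysis and takes those scans out of the offset.

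**After the change.** With the interpretable offset the model rate matches the unadjusted rate: 0.0497 against 0.0497 at a true rate of 0.05 and *u* = 5%.

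**The case against.** The strongest reply is that *received* is loose wording. It stands under a bullet limited to Weeks 24, 48 and 96 and repeats the protocol's phrase. A programmer may well count only interpretable scans at those visits, and the bias is then zero. This limits the point to the text as written. But the SAP says interpretable where it means it, a few lines earlier and again for T2 lesion volume, so the offset should say so too.

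It is also true that the unadjusted rate, correctly scaled, is reported alongside. The two rates will differ anyway because of the covariates, so a gap between them would not by itself show this problem.

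A reader might infer more than the documents support:

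- **Scans for suspected PML inflate the offset.** SAP 4.4 already keeps unscheduled scans of this kind out of the efficacy analyses, and the protocol's schedule allows off-schedule MRI only for that reason.
- **Early-withdrawal scans inflate the offset.** At discontinuation, "all assessments must be completed/obtained, except for MRI if done within the past 8 weeks unless clinically indicated". The protocol's exclusion, "Data from other unscheduled assessments will not be included in this summary or analysis", does not clearly reach this visit, which has its own column in the schedule. SAP 4.4 applies visit windows defined in Module 2, which is not among the documents. A withdrawal scan may be placed at Week 24, 48 or 96 and then count on both sides.
- **The baseline scan is counted.** The offset is there because the number of scans varies between patients. The baseline scan is mandatory, baseline Gd status is a covariate, and the rate covers only the three later visits.

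**Conclusion.** The offset is wrong as written, and the point is minor. If it is programmed literally, the adjusted T1 Gd rate is low by about the share of received Week 24, 48 and 96 scans that cannot be read: about 1–2% at a 1–2% share, 5% at 5% and 9–10% at 10%. The T2 lesion rate is exposed in the same way through the shared method.

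These sizes rest on assumed shares and on unreadability being unrelated to lesions. A reader might conclude that the adjusted rate is certain to be biased. The documents do not support that, because the bias is zero if every scan is readable or if the program counts only interpretable scans.

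The endpoints are secondary and descriptive in a single-arm study. The primary endpoint and the sample size do not depend on them.

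**What to change.** In SAP 4.4.2, define the offset as the log number of interpretable post-baseline scans at Weeks 24, 48 and 96, after visit windowing, that contribute to the lesion count. These are the same scans as in the unadjusted denominator. State that a withdrawal scan enters both the count and the offset, or neither. Apply the same rule to new or enlarging T2 lesions.

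The cost is one phrase for the offset and a sentence on withdrawal scans, with no new data. The adjusted rate may come out slightly higher, and so slightly less favourable, than under the literal wording.

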#### **Total number of new and/or enlarging T2 lesions detected by brain MRI at weeks 24, 48, and 96**

The analyses of this outcome will be similar to the analyses of total T1 Gd-enhanced lesions as described above.

The mean change in total T2 lesion volume detected by brain MRI from baseline to Weeks 24, 48, and 96 will be analyzed using a longitudinal mixed effects model repeated measure (MMRM). The model's fixed effects will include visit along with the following baseline covariates: baseline T2 lesion volume, number of previous DMTs (1 vs. >1), baseline T2 lesion volume by visit interaction, and baseline EDSS score (< 2.5 vs.  $\geq$  2.5). Visit will be treated as a repeated variable within a patient. Patient and visit will be treated as factor variables. An unstructured variance-covariance structure will be applied to model the within-patient errors. The model will be fitted using the Restricted Maximum Likelihood method (REML). Denominator degrees of freedom will be estimated using Satterthwaite's approximation. Any patient with an interpretable post baseline MRI will be included in the model.

A plot of T2 lesion volume least squares mean changes from baseline over time and corresponding 95% confidence intervals will be presented.

#### **4.4.3 Exploratory Efficacy Endpoints**

The ITT population will be used for exploratory efficacy endpoints.

Changes from baseline in EDSS scores at Weeks 24, 48, and 96 will be estimated using a longitudinal mixed effects model repeated measure (MMRM). The model's fixed effects will include visit along with the following baseline covariates: baseline EDSS score and number of previous DMTs (1 vs. >1), baseline EDSS score by visit interaction. Visit will be treated as a repeated variable within a patient. Patient and visit will be treated as factor variables. An unstructured variance-covariance structure will be applied to model the within-patient errors. The model will be fitted using the Restricted Maximum Likelihood method (REML). Denominator degrees of freedom will be estimated using Satterthwaite's approximation.

A plot of the adjusted mean EDSS changes from baseline will be produced.

Percent changes from baseline in brain volume at Weeks 24, 48, and 96 will be estimated using the same model as the T2 lesion volume in section 4.4.2.

Change in below PROs from baseline will be estimated using MMRM adjusting for visit along with following baseline covariates: baseline score and number of previous DMTs

(1 vs. >1), baseline EDSS score (<2.5 vs. >=2.5) and baseline PRO score by visit interaction. Visit will be treated as a repeated variable within a patient. Patient and visit will be treated as factor variables.

- MSIS-29 - The Multiple Sclerosis Impact Scale
- SATMED-q - The Treatment Satisfaction with Medicines Questionnaire
- TSQM II - The Treatment Satisfaction Questionnaire for Medication Version II

Detailed analysis method for the PRO endpoints will be described in [Section 4.6](#).

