- ^l Serum or urine β -hCG must be performed at screening in women of childbearing potential within 14 days prior to initiation of study drug. Subsequently, urine β -hCG (sensitivity >25 mIU/mL) must be collected. On infusion visits, the urine pregnancy test should be performed prior to premedication in all women of childbearing potential. If positive, ocrelizumab should be withheld and pregnancy status confirmed.
- ^m All patients must have negative HBsAg result and negative HepCAb screening tests prior to enrollment in the study. If the total HBcAb is positive at screening, HBV DNA measured by PCR must be negative in order for a patient to be eligible for the study. For enrolled patients with negative HBsAg and positive total HBcAb, HBV DNA (by PCR) must be repeated every 24 weeks.
- ⁿ Whole-blood samples will be collected to determine the duration of B-cell depletion and recovery (CD19+) and T-cell counts (CD4+, CD8+).
- ^o To be obtained/Performed before administration of ocrelizumab (i.e., pre-dose).

Ocrelizumab—Genentech, Inc.
77/ Protocol MN30035, Version 5

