## **2. STUDY DESIGN**

This study is a prospective, multicenter, open-label, effectiveness and safety study in patients with RRMS who have had a suboptimal response to an adequate course of a DMT. This study will be conducted in North America.

An adequate course of prior DMT is defined as the same DMT administered for at least 6 months. Ocrelizumab will be administered as an initial dose of two 300-mg infusions (600 mg total) separated by 14 days (i.e., Days 1 and 15) followed by one 600-mg infusion every 24 weeks for the study duration.

Patients will be assessed for effectiveness and safety every 24 weeks as described in the schedule of assessment in [Appendix 2](#).

The study will consist of the following periods, described in detail below:

1. Screening period: up to 4 weeks.
2. Treatment period: open-label treatment period of 96 weeks (4 doses).
3. Safety follow-up period (additional B cell monitoring not applicable to protocol v5 patients): observation after the last infusion of study drug for patients who discontinue or who chose not to continue with commercially available ocrelizumab (if approved) at the end of study.
4. Eligible patients can be enrolled into an optional shorter infusion substudy to explore the effect of a shorter infusion of ocrelizumab on the rate and severity of IRRs.

Detailed study design, outcome measures and statistical analysis plan of the shorter infusion substudy will be described in Appendix 6.

[figure not shown]

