### **2.2.3 Exploratory Efficacy Outcome Measures**

- Change in neurological exam score (EDSS) at Weeks 24, 48 and 96 from baseline
- Percent change in brain volume at Weeks 24, 48, and 96 from baseline
- Change in Patients Reported Outcome Scales from baseline:
  - MSIS-29 - The Multiple Sclerosis Impact Scale
  - SATMED-q - The Treatment Satisfaction with Medicines Questionnaire
  - TSQM II - The Treatment Satisfaction Questionnaire for Medication Version II

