#### **4.6.1 MSIS-29**

The Multiple Sclerosis Impact Scale (MSIS-29) is a 29-item questionnaire designed to measure the physical and psychological impact of MS from the patient's perspective.

| Dimension           | Items | Item Scores   |
|---------------------|-------|---|
| Physical Scale      | 1-20  | 1 = Not at all
2 = A little
3 = Moderately
4 = Extremely |
| Psychological Scale | 21-29 | 1 = Not at all
2 = A little                                    |

|  |  |                |
|--|--|----------------|
|  |  | 3 = Moderately |
|  |  | 4 = Extremely  |

Score for the physical scale is calculated as follows:

- Items 1-20 are added
- A transformed score =  $100 \times (\text{observed score} - 20) / (80-20)$  is derived

Score for the psychological scale is calculated as follows:

- Items 21-29 are added
- A transformed score =  $100 \times (\text{observed score} - 9) / (36-9)$  is derived

Higher scale values indicate higher impact of MS disability on the patient. Missing scores in the specific scale are not imputed.

MSIS-29 results by dimension will be summarized for baseline and weeks 24, 48, 72, and 96 visits. The mean change in each MSIS-29 dimension score from baseline to weeks 24, 48, and 96 will be analyzed using a longitudinal mixed effects model repeated measure (MMRM). The fixed effects will include visit along with the following baseline covariates: baseline MSIS-29 score, number of previous DMTs (1 vs >1), baseline MSIS-29 score by visit interaction, and baseline EDSS score (< 2.5 vs.  $\geq 2.5$ ). Visit will be treated as a repeated variable within a patient. Patient and visit will be treated as factor variables. An unstructured variance-covariance structure will be applied to model the within-patient errors. The model will be fitted using the Restricted Maximum Likelihood method (REML). Denominator degrees of freedom will be estimated using Satterthwaite's approximation.

A plot of the least squares mean changes from baseline in MSIS-29 scores over time and the corresponding 95% confidence intervals will be presented for each dimension of the scale.

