#### **4.6.2 SATMED-q**

The Treatment Satisfaction with Medicines Questionnaire includes 17 questions scored on a 5-point Likert-type scale investigating the following dimensions. The bolded dimensions will be summarized:

| Dimension                       | Items | Item Scores  |
|---------------------------------|-------|--|
| Any Undesirable side effects    | 1     | 0=No
1=Yes                                      |
| Undesirable Side effects | 1-3   | 4 = Not at all
3 = A little bit
2 = Somewhat |

|                                   |       |  |
|-----------------------------------|-------|--|
|                                   |       | 1 = Quite a bit
0 = Very much   |
| Treatment effectiveness    | 4-6   | 0 = Not at all
1 = A little bit
2 = Somewhat
3 = Quite a bit
4 = Very much |
| Convenience for use        | 7-9   | 0 = Not at all
1 = A little bit
2 = Somewhat
3 = Quite a bit
4 = Very much |
| Impact on daily activities | 10-12 | 0 = Not at all
1 = A little bit
2 = Somewhat
3 = Quite a bit
4 = Very much |
| Medical care                      | 13-14 | 0 = Not at all
1 = A little bit
2 = Somewhat
3 = Quite a bit
4 = Very much |
| Global satisfaction               | 15-17 | 0 = Not at all
1 = A little bit
2 = Somewhat
3 = Quite a bit
4 = Very much |

Items are summed to yield the dimension scores. Higher scores indicate higher satisfaction with treatment. Missing score should be substituted by the worst possible score where applicable (items 1 to 3: if question “Have you experienced any undesired effects caused by the medicine” = “Y”, then missing=“Quite a bit”, otherwise missing will not be imputed; items 4 to 17: missing=“Not at all”). If two or more answers are missing in a given dimension, the dimension should be discarded. If two contiguous response categories are selected for one item, the worst score should be selected as valid. When two non-contiguous response categories are selected, the response should be considered as missing.

Analysis of the SATMED-q scores will be based on a longitudinal MMRM similar to the planned analyses of the MSIS-29 scores as described above.

A plot of the least squares mean changes from baseline in SATMED-q scores over time and the corresponding 95% confidence intervals will be presented for each bolded dimension of the scale.

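### The repeated-measures models for the PROs, and on the natural reading EDSS, leave out the Week 72 visit although it is collected; adding it is a free, small improvement to exploratory analyses

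*SAP*

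**What the plan says.** **Collection.** SAP Section 2 states: "Patients will be assessed for effectiveness and safety every 24 weeks". The schedules in Protocol Appendix 1 and SAP Appendix 2 both mark EDSS and the PROs at Week 72. Neither marks a brain MRI at that visit.

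**MSIS-29.** SAP 4.6.1 has two adjacent sentences with different visit lists. The descriptive one reads "MSIS-29 results by dimension will be summarized for baseline and weeks 24, 48, 72, and 96 visits". The model sentence reads "The mean change in each MSIS-29 dimension score from baseline to weeks 24, 48, and 96 will be analyzed". Protocol 6.5.4 uses the same three weeks for the PRO models.

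**Other PROs.** SAP 4.6.2 states: "Analysis of the SATMED-q scores will be based on a longitudinal MMRM similar to the planned analyses of the MSIS-29 scores". SAP 4.6.3 refers TSQM II to the MSIS-29 model in the same way. The general PRO paragraph in SAP 4.4.3 names no weeks.

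**EDSS.** SAP 2.2.3 defines the outcome as "Change in neurological exam score (EDSS) at Weeks 24, 48 and 96 from baseline", and SAP 4.4.3 carries those three weeks into the model description: "Changes from baseline in EDSS scores at Weeks 24, 48, and 96 will be estimated".

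**Model.** Visit is a factor, and the EDSS and MSIS-29 models specify unstructured covariance and REML. The population is ITT, which keeps early withdrawals.

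**The concern.** The list of Weeks 24, 48 and 96 suits MRI, which has no Week 72 scan. It does not suit EDSS or the PROs, and no reason is given for dropping a collected visit.

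An MMRM handles a missing Week 96 value by predicting it, in effect, from the visits and covariates in the model. It is valid if missingness depends only on those. For a patient who leaves after Week 72, the most recent score is the Week 72 one. If that score influences leaving, missing at random can hold with Week 72 in the model and generally fails without it. If patients doing worse at Week 72 leave, the Week 96 mean looks too favourable: worsening on EDSS and MSIS-29 is understated and satisfaction is overstated. In a single-arm study no control arm offsets this.

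The second cost is precision, and it also comes from patients without a Week 96 value. Where Week 96 is observed, Week 72 adds practically nothing to the Week 96 estimate.

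**Working it through.** **Inputs.** The plan gives no figure for these models. From the documents I use only N = 600, which sets the scale of the standard error. Protocol 6.1's 598.86, rounded to 600, reproduces: with a Wald interval and exact binomial probabilities the smallest n is 598. It is not in dispute.

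Everything else is assumed, because the documents give no late dropout rate, SD or correlation:

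- SD of change = 1, so results are in SD units;
- AR(1) correlation ρ = 0.6 to 0.8 per 24 weeks;
- log-odds of leaving after Week 72 rise by β = ln 2 = 0.693 per SD of the Week 72 change;
- earlier visits are complete;
- proportion d without Week 96 is 2% to 12%.

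The nearest figure in the documents is 3.5% stopping treatment for adverse events over 96 weeks in the pooled RMS Phase III studies (Protocol 1.2.1.2). It covers one reason only, so it is neither an estimate of d nor a ceiling.

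**Bias without Week 72.** To first order, selection shifts the mean Week 72 score of those who stay by −βd. The part that Weeks 24 and 48 cannot explain passes to Week 96 through the conditional covariance, which under AR(1) is ρ(1 − ρ²). So

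bias ≈ −d × β × ρ × (1 − ρ²).

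- ρ = 0.6: 0.693 × 0.6 × 0.64 = 0.266 per unit d
- ρ = 0.8: 0.693 × 0.8 × 0.36 = 0.200 per unit d

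| d | Size of bias, ρ = 0.8 (SD) | Size of bias, ρ = 0.6 (SD) |
|---|---|---|
| 2% | 0.004 | 0.005 |
| 3.5% | 0.007 | 0.009 |
| 5% | 0.010 | 0.013 |
| 12% | 0.024 | 0.032 |

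Simulation agrees: 0.024 to 0.031 SD at 12%. One standard error at N = 600 is about 1/√600 = 0.041 SD. The bias is therefore about 0.1 to 0.3 standard errors at 2% to 5%, and about 0.6 to 0.75 at 12%.

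**Other correlation structures.** A second simulation used compound symmetry (0.5, 0.7) and AR(1) (0.7, 0.85), with β of 0.5 or 1.0. The bias was 0.001 to 0.017 SD at 2% to 5% missing, 0.006 to 0.033 SD at 10%, and 0.009 to 0.050 SD at 15%. With β = 0 it was zero within simulation error. With Week 72 in the model it was at most 0.0004 SD throughout.

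**Variance.** Var = (1 − R²)/(N(1 − d)) + R²/N, where R² is the share of Week 96 variance explained by the earlier visits in the model. For AR(1) with ρ = 0.7 and d = 15%:

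- without Week 72, R² = 0.7⁴ = 0.24: 0.76/0.85 + 0.24 = 1.134 (times 1/N)
- with Week 72, R² = 0.7² = 0.49: 0.51/0.85 + 0.49 = 1.090 (times 1/N)
- ratio 1.134/1.090 = 1.040

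Across all scenarios of the second simulation the ratio was 1.001 to 1.040, a gain of about 0.1% to 4%.

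**The case against.** **Exclusion is not stated outright for EDSS.** The sentence in SAP 4.4.3 can be read as naming the time points to be reported, with every scheduled visit still in the model. Visit windows are in Module 2, which is not among the documents. This stands: for EDSS the plan is unclear, not demonstrably wrong. It carries little weight for MSIS-29, where SAP 4.6.1 includes Week 72 in one list and omits it from the next.

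**The mechanism is assumed, and the simulations favour the fix.** Leaving was made to depend only on the Week 72 score, so the model containing Week 72 is unbiased by construction. If leaving depends only on Weeks 24 and 48 there is nothing to correct. If it depends on events after Week 72, adding the visit will not remove the bias fully. This also stands.

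**Late leavers may still supply data.** Protocol Appendix 1 requires all assessments when treatment is discontinued, with an exception only for a recent MRI. Follow-up after the Week 72 infusion falls at Week 96. Depending on the unseen windows, some leavers will have a usable late value, which would shrink the effect.

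**The SAP follows the protocol.** Protocol 6.5.4 sets the same three weeks for the PRO models. That explains the list but gives no reason to discard a collected visit.

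A reader might also infer that Week 96 is the main time point for these endpoints. The documents do not say so: where weeks are named, 24, 48 and 96 have equal standing.

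**Conclusion.** The point holds as a minor improvement. For the three PROs, a collected visit is left out of a likelihood model that relies on missing at random. For EDSS the same reading is the natural one but not certain.

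Under the assumptions above (odds doubling per SD, AR(1) correlation of 0.6 to 0.8), the Week 96 bias is about 0.004 to 0.013 SD at 2% to 5% late missingness and 0.024 to 0.031 SD at 12%. It is zero if leaving is unrelated to the Week 72 value. The variance gain is about 0.1% to 4%.

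Three stronger readings are tempting but unsupported:

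- *That late dropout is high enough to distort the results.* No rate for Weeks 72 to 96 is given, and 12% is an assumption at the upper end of the range in the table.
- *That the main conclusions are at risk.* These endpoints are exploratory. The primary endpoint does not use these models, and confirmed progression is assessed on EDSS at scheduled visits including Week 72.
- *That the T2-volume and brain-volume models share the flaw.* No MRI is scheduled at Week 72, so their list is complete.

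**What to change.** State in SAP 4.4.3 and 4.6 that the MMRMs for EDSS, MSIS-29, SATMED-q and TSQM II use all scheduled post-baseline visits (Weeks 24, 48, 72 and 96), with estimates still reported at Weeks 24, 48 and 96. Leave the T2-volume and brain-volume models unchanged.

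The SAP should note this as a clarification of the visit list for the PRO models in Protocol 6.5.4. It needs no new data and leaves the reported time points as they are. The cost is a sentence of text and one more visit level; the unstructured covariance matrix grows from 3 × 4/2 = 6 to 4 × 5/2 = 10 parameters, which is no burden with about 600 patients.
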